2. INTRODUCTION

2.1 STUDY RATIONALE

In this study, the novel compound RO7296682, which selectively binds to CD25 (the IL-2 receptor α chain) while not interfering with interleukin-2 (IL-2) signaling, will be assessed as a T-regulatory cell (Treg)-depleting strategy for the treatment of cancer. Tregs can suppress antigen-specific, anti-tumor immune responses, thus allowing for tumor growth. Reducing the number of Tregs, or fully removing Tregs from tumors, may reduce tumor growth in vivo and may foster or restore an immune response to tumor cells in humans.

RO7296682 is a glycoengineered monoclonal antibody (mAb) against CD25. It is designed to mediate Fc γ RIIIa-dependent, CD25-targeted cell cytotoxicity (aka, antibody-dependent cellular cytotoxicity [ADCC]) and antibody-dependent cellular phagocytosis (ADCP). The Fc region of RO7296682 is afucosylated to increase Fc γ RIIIa affinity, and, thus, to outcompete human IgG1 isotypes and trigger ADCC more effectively ([Buettner et al. 2018](#), and [Kellner et al. 2017](#)).

CD25 is a highly expressed cell surface lineage marker of Tregs and is critical for their survival ([Sakaguchi et al. 2008](#)). The high prevalence of CD25 on Tregs, as well as a >20 to 100-fold higher expression of CD25 on Tregs vs. cytotoxic T lymphocytes (CTLs), qualifies CD25 as superior target over other Treg markers. Other T-cell markers (such as CCR4 or Ox40) have a lower prevalence on Tregs with a more uniform and indiscriminate expression on CTLs and Tregs.

RO7296682 has low affinity to CD25 and relies on avidity for effective binding. This results in preferential binding to Tregs, which are CD25 high, while it spares CD25 low expressing cells such as CTLs. An additional key feature of RO7296682 is that it binds CD25 while not blocking IL-2 signaling, particularly in activated Tregs (see Section 2.1 of [RO7296682 Investigator's Brochure \(IB\)](#) for details). Therefore, RO7296682 has the potential to improve anti-cancer outcomes, particularly in combination with other immune-modifying agents

In this first-in-human, open-label, multicenter Phase 1 study, WP41188, the safety and tolerability of RO7296682 will be explored and the Maximum Tolerated Dose (MTD) and/or Recommended Phase 2 Dose (RP2D) will be determined. Study WP41188 will also assess the pharmacokinetics (PK), pharmacodynamics (PD), and preliminary anti-tumor activity of RO7296682. RO7296682 will initially be explored in non-small cell lung cancer (NSCLC), melanoma (MEL), head and neck squamous cell carcinoma (HNSCC), ovarian cancer (OvC), triple-negative breast cancer (TNBC), and esophageal carcinoma (EsC). The rationale for the study design is provided in Section [4.2](#).

2.2 BACKGROUND

[figure not shown]
Tregs have been postulated to be one of the major suppressive factors in the tumor microenvironment and their presence is linked to poor outcomes in many tumors (see e.g. [Togashi et al. 2019](#)). Although checkpoint inhibitors (CPIs) have led to major improvements in patient outcomes, particularly in NSCLC and MEL, many patients do not respond to therapy, have a suboptimal response, or relapse after a period of response. The mechanisms behind resistance or relapse are still incompletely understood. Immunosuppressive effects mediated by Tregs are among the main mechanisms under discussion and investigation ([Sharma et al. 2017](#)).

High levels of Tregs are associated with poor prognoses in several human cancers, such as NSCLC and MEL ([Jenkins et al. 2018](#), [Fridman et al. 2012](#), [Liu et al. 2016](#)). RO7296682 was designed to selectively deplete CD25-high Tregs via enhanced ADCC while not interfering with IL-2-mediated Teff signaling. A detailed description of the chemistry, pharmacology, and safety of RO7296682 is provided in the [RO7296682 IB](#).

2.3 BENEFIT/RISK ASSESSMENT

RO7296682 is hypothesized to provide a significantly improved chance of addressing the large unmet medical need that remains for many cancer patients, including CPI-naïve and CPI-experienced/resistant patients. Depleting CD25-expressing Tregs without impacting the number and function of T-effectors, and without interfering with IL2 signaling, has the potential to translate into clinical benefit in cancer patients.

Due to its characteristics, RO7296682 is expected to shift the overall balance of the tumor immune system into a condition enhancing the probability to have an immune response against the tumor. Available non-clinical data demonstrate that RO7296682 or its mouse surrogate is active and induces tumor reduction in different tumor mouse models as well as depletes Tregs in peripheral blood and tissues.

This is the first study in which RO7296682 will be administered to humans and as such, its actual dose risks are unknown. It is anticipated that the safety profile of RO7296682 will be distinct from previously generated anti-CD25 compounds that were originally designed to reduce the number of Teffs and thereby (in contrast to RO7296682) act as immunosuppressive agents.

Potential risks anticipated with RO7296682 may be related to its immune enhancing effects (i.e. immune-related toxicity) and to the depletion of the resident Tregs,

particularly in the skin, where it was demonstrated that Tregs play a role in the skin barrier and in the wound healing process (Ali and Rosenblum 2017) See also corresponding section on potential risks in the [RO7296682 IB](#).

In summary, Tregs are considered one of the resistance mechanism of the antitumor immune response. Targeting Tregs through RO7296682 therefore has the potential to provide substantial anti-tumor immune response via a change in the Teff/Treg ratio and may also enable a multitude of combinations with other immunotherapies or with established anti-cancer agents for future clinical development. The existing nonclinical data with RO7296682 provides an acceptable risk-benefit balance for the clinical investigation of RO7296682 in patients with advanced cancers who have progressed on a cancer therapy for whom no effective standard therapy exists.

3. OBJECTIVES AND ENDPOINTS

The objectives and corresponding endpoints are provided in [Table 3](#).

Table 3 Objectives and Endpoints

Objectives	Endpoints
Primary	
To characterize the safety, tolerability, maximum-tolerated dose (MTD) and/or Recommended Phase 2 Dose (RP2D) of RO7296682	
 • Nature and frequency of AEs (with severity determined according to the National Cancer Institute Common Terminology Criteria for Adverse Events [NCI CTCAE] v5.0) • Nature and frequency of dose-limiting toxicities (DLTs)
Secondary	
To assess the preliminary anti-tumor activity of RO7296682	
 • Objective response rate (ORR) • Disease control rate (DCR); defined as ORR + stable disease [SD] rate • Duration of response (DoR) • Progression-free survival (PFS) 
All according to the Response Evaluation Criteria in Solid Tumors (RECIST) Version 1.1

Objectives	Endpoints
To investigate the PK profile of RO7296682	PK profiles and parameters derived for RO7296682 including but not limited to: 
 • Area under the curve (AUC), minimum concentration (C_{min}), maximum concentration (C_{max}), Clearance (CL), Volume of distribution at steady-state conditions (V_{ss}), Half-life ($t_{1/2}$), as appropriate, Time of maximum concentration (T_{max})
To evaluate the anti-drug immune response after treatment	
 • Incidence and titer of ADA during the study relative to the prevalence of ADA at baseline
To assess the PD effect of RO7296682 in blood and tumor tissue	
 • Treatment-induced changes in Treg levels in blood and/or tumor as compared to baseline. • Treatment-induced changes in Treg/Teff ratio in blood and/or tumor as compared to baseline.
Exploratory	
To characterize PD effects and duration of PD response following RO7296682 administration	
 • Changes in number, frequency, activation status, and distribution of blood and tumor infiltrating lymphocytes (TILs)
To evaluate the relationship between RO7296682 exposure and PD biomarkers	
To evaluate preliminary anti-tumor activity of RO7296682 according to immune RECIST (iRECIST)	
 • Objective response rate (ORR) • Disease control rate (DCR); defined as ORR + SD rate All according to immune RECIST (iRECIST) 
In addition:
 
 • Duration of response (DoR) • Progression free survival (PFS) • Overall survival (OS) if data are mature
To explore potential effects of ADA	
 • Relationship between ADA status and PK/PD, safety, and efficacy

Objectives	Endpoints
To explore biologic markers that might act as predictors of safety and/or anti-tumor activity of RO7296682	
To explore degree of target binding of RO7296682 (in association with PK) via a receptor occupancy (RO) assay	
 Evaluate RO via ex-vivo assay
To explore the effect of Treg depletion in the skin immune contexture	
 Treatment-induced changes in Treg levels in the skin as compared to baseline.
To explore the effect of Treg depletion on the gut microbiome	
 Treatment-induced changes of the gut microbiome as compared to baseline

4. STUDY DESIGN

4.1 OVERALL DESIGN

- Study WP41188 is a first-in-human, open-label, multicenter, Phase 1 dose escalation study of single agent RO7296682 in participants with advanced and/or metastatic NSCLC, MEL, HNSCC, OvC, TNBC, or EsC. An overview of the study design is provided in Section 1.2.

All participants will be treated with RO7296682 until disease progression, unacceptable toxicities, withdrawal of consent, or withdrawal of the participant by the Investigator. Participants may continue treatment with RO7296682 for a maximum of 24 months. This period may be adjusted based on the emerging safety and response profile. As with other immunotherapies, treatment beyond progressive disease (i.e. due to pseudo-progression) according to RECIST Version 1.1 can be considered after initial dose, following consultation and agreement between the Sponsor and Investigator.

[figure not shown]
For the maximum number of participants, please refer to Section 9.2.

The study consists of 2 parts: Part A is a single agent dose escalation and Part B is a single agent dose expansion.

- Part A: RO7296682 dose escalation in multiple participant cohorts**

Part A will determine the safety, tolerability, PK/PD profile, and preliminary anti-tumor activity of escalating doses of RO7296682 using a minimum of 3 DLT evaluable participants per cohort (see Section 9.3 for definition of DLT analysis population). The starting dose will be 0.3 mg and the maximum dose is planned to be 500 mg. Participants will receive intravenous (IV) RO7296682 every 3 weeks (Q3W) and the cycle length will be accordingly defined as 21 days. Incremental increases (and potential decreases) between cohorts will be determined by a Bayesian-based continuous reassessment method (CRM) with overdose control measures. Entry into a cohort will be controlled by a 7-day safety window between participants 1 and 2 in each cohort. Please refer to Section 4.1.2.1 for details on the DLT window. At least 3 DLT evaluable participants will be enrolled in each Part A cohort during the dose escalation. For intra-patient dose escalation, please refer to Section 4.1.2.2.

Part A will enroll participants with NSCLC, MEL, OvC, HNSCC, TNBC, or EsC who have progressed on all standard therapies, are intolerant to standard of care (SOC), and/or are non-amenable to SOC, or for whom SOC does not exist.

The criteria to start collecting on-treatment biopsies may be changed based on emerging data through a protocol amendment. Such biopsies will be collected, provided they are clinically feasible, lesions are accessible, and the participant's consent for these biopsies has been obtained. This will be agreed upon between the Sponsor and Investigators. Part A will determine the MTD and/or RP2D based on the safety, tolerability, and PK/PD profile of RO7296682. The maximum total number of participants in Part A will consist of approximately 90 DLT evaluable participants.

- **Part B: RO7296682 single agent dose expansion cohort:**

Part B will evaluate safety, tolerability, PK/PD profile, and preliminary anti-tumor activity of the MTD and/or RP2D of RO7296682 determined in Part A in participants with MEL, NSCLC, and HNSCC. Approximately 20 evaluable paired tumor biopsy samples will be obtained. Part B will conclude when approximately 20 evaluable paired tumor biopsy samples or a maximum total number of 50 participants has been reached.

Note: If evolving safety and PK/PD data suggest so, tumor types other than those now indicated will be evaluated. In that case, the exact solid tumor indication(s)

inclusion/exclusion criteria, and schedule of activities will be specified in a substantial protocol amendment.

4.1.1 Length of the Study

The maximum duration of the study for each participant will be up to 28 months, divided as follows:

- Screening: Days –28 to –1
- Treatment Period: C1D1 to Month 24 (may be modified if supported by emerging data)
- End of Treatment Visit: 28 (\pm 7) days after last dose (see Section 4.4)
- Safety follow-up: 90 (\pm 7) days after last treatment with RO7296682
- Survival follow-up: 90 (\pm 7) days after the safety follow-up visit; then every 3 months (\pm 14 days) until death, lost to follow-up or until study closure by the Sponsor, whichever occurs first.

4.1.2 Dose-Escalation Decision Criteria: Part A

Dose-escalation will be carried out according to a modified continual reassessment method (mCRM) with escalation with overdose control (EWOC) design and dose levels selected will be based on the occurrence of DLTs. This model-based design assigns participants to dose levels and defines the MTD based on the estimation of the target toxicity level by a model depicting the dose-toxicity relationship.

[REDACTED]

4.1.2.1 Part A: Single Agent Dose Escalation

The primary objective of Part A will be to determine the MTD and/or RP2D and DLT profile in multiple participant cohorts. Part A starts with an initial dose of 0.3 mg (see Section 4.3 for dose justification).

[REDACTED]

The DLT period starts from the first administration of RO7296682 and ends 7 days after the second administration of RO7296682. [REDACTED]

The first participant at each dose level must have completed at least 7 days from the first dose without DLT before the second participant can be treated at this dose level. If the first participant experiences a DLT within the first 7 days of treatment, a period of at least 7 days must be maintained between the second and third participants. This pattern must be maintained for subsequent participants until a period of at least 7 days without a DLT has been completed between participants. Once this is achieved, all subsequent participants in a cohort can be enrolled, with no fixed observation period between participants. After the third evaluable participant in each cohort has completed the DLT observation period, the logistic regression model will be updated with the treatment outcome (i.e., the occurrence of DLT) and a new estimate of the MTD will be derived and the recommended dose will be either the new estimate of the MTD or the maximum dose allowed by safety constraints. Selection of the new dose level must be agreed by the Investigator and the Sponsor, as well as being guided by the EWOC recommendation. Please refer to Section 4.1.5 for the communication strategy.

The design will continue as described, assigning participants to the current maximal dose allowed as estimated from all of the DLT data cumulatively, until one of the pre-defined stopping criteria are satisfied (see Section 4.1.4) or the pre-determined sample is reached, whichever comes first.

Built-in safety constraints are in place to prevent exposing participants to undue risk of toxicity:

- [REDACTED] – see also the [RO7296682 IB](#). Indeed, a 3-fold has been assumed in a recent Food and Drug Administration (FDA) Oncology review of first-in-human studies for immune-activating agents as it is approximately equivalent to half-log dose increment, which is a common approach for biologics and was also the approach observed for the majority of investigational new drugs in the dataset for the first few escalation steps ([Saber et al. 2017](#)). In the absence of DLTs a further increase of 10% of the 3-fold cap (i.e. 3.3-fold vs. 3-fold) will be considered within the allowed built-in safety constraints if the resulting dose increment lead to a dose level which can be more easily administered to the patient (example: 1 mg instead of 0.9 mg).

- In absence of a DLT a dose increment of 200% is allowed (i.e., next dose could be as high as 3-fold the previous dose)
- After 1 DLT has been observed, a dose increment of up to 100% (i.e. up to 2-fold) is allowed.

If deemed necessary to further characterize the safety, PK, and/or PD profile of RO7296682, additional participants may be enrolled.

For the definition of the SDEC, see [Appendix 1](#).

Part A Single Agent dose escalation may be halted prior to identification of MTD and upon sufficient characterization of the investigational medicinal product in regards to safety, PK, and PD.

4.1.2.2 Individual Dose Increase for Participants in a Dose-Escalation Cohort

At the discretion of the Investigator and in agreement with the Sponsor, intra-patient dose escalation for individual participants treated at lower RO7296682 doses may be considered for treatment at higher doses of RO7296682 than those allocated at the time of enrollment, if the dose is considered safe. Thus, after completing at least 9 weeks on treatment or after the first tumor assessment whichever comes first, at one dose level with no major safety concerns, a participant may receive a higher RO7296682 dose level at the next scheduled cycle within the participant's dosing schedule, which is at least one dose level below the highest currently evaluated dose or up to the MTD and/or the RP2D of RO7296682, if reached.

If intra-participant dose-escalation for an individual participant is considered, treatment must be administered as indicated in Section [6.1.1](#) as if it was the first administration to the study participant (i.e. 4 h infusion for the first higher dose of RO7296682).

4.1.3 Dose-Limiting Toxicities

A DLT is defined as a clinically significant AE (classified according to the NCI CTCAE v.5.0, as applicable) or significant laboratory abnormality if all of the following events apply:

- occurring during the DLT assessment period as defined in Section [4.1.2.1](#); and
- considered to be related to study treatment RO7296682 by the Investigator, and
- is not attributed to disease progression or another clearly identifiable cause

During the dose escalation phase, participants who withdraw before the end of the DLT period, for reasons other than DLTs, and participants who did not receive two doses of RO7296682 will be replaced to ensure that at least 3 DLT evaluable participants have been assessed prior to moving to the next dose level (see Section 7.1 for replacement rules). The DLT will be counted for each dose separately and each participant will contribute one single representative data point to the EWOC design.

The following AEs are considered DLTs:

Hematological toxicities defined as:

- Grade 4 neutropenia (ANC of $<500/\mu\text{L}$) lasting ≥ 7 days
- Grade ≥ 3 febrile neutropenia
- Grade 4 thrombocytopenia lasting ≥ 48 hours
- Grade 3 thrombocytopenia associated with significant bleeding episode and/or bleeding episodes requiring platelet transfusions
- Grade 4 anemia

Any non-Hematological toxicities Grade ≥ 3 except for:

- Grade 3 nausea, vomiting, or diarrhea that resolves to Grade ≤ 1 with or without treatment and which resolves within one week
- Grade ≥ 3 fatigue that resolves to Grade ≤ 2 within 7 days
- Grade 3 arthralgia that can be adequately managed with supportive care or that resolves to Grade ≤ 2 within 1 week
- Fever >40 degrees Celsius that occurs within 48 hours of RO7296682 infusion and resolves to $<$ Grade 2 within 48 hours and is fully resolved within 7 days
- Grade ≥ 3 laboratory abnormality that is asymptomatic and deemed by the Investigator not to be clinically significant
- Grade 3 autoimmune thyroiditis or other endocrine abnormality that can be managed by endocrine therapy or hormonal replacement
- Grade 3 tumor flare defined as local pain, irritation, or rash localized at sites of known or suspected tumor
- Grade 3 transient increase of bilirubin in participants with liver lesions, transaminases (aspartate aminotransferase [AST]/alanine aminotransferase [ALT]) and/or gamma-glutamyl transferase (GGT) that starts within 24 hours of infusion and recovers to Grade 1 or baseline within one week.

Additional DLTs not fulfilling the above criteria

- Any other RO7296682-related toxicity considered significant enough to be qualified as a DLT in the opinion of the Investigator after discussion with the Sponsor.

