e)	Complete neurological exam: Neurologic examinations should include an assessment of mental status, cranial nerves, muscle strength, sensation, and coordination. Results of the neurological exam should be documented in the participant's chart. Mental status checks do not require completion of a validated mental status questionnaire.
f)	Stool samples (optional): Only collected in Part B, dose expansion and provided participant signed the consent for optional stool samples. For details on when samples should be collected, refer to Section 8.9.
g)	Vital signs: please refer to the hourly Table 2 for details.
h)	Optional safety visits Optional safety visits upon discretion of the Investigator.
i)	Targeted physical/neurological examinations: Examinations should be limited to systems of primary relevance (i.e., cardiovascular, respiratory, neurologic, and any system that might be associated with tumor assessment [e.g., lymph nodes, liver, and spleen and those systems associated with symptoms], or potential drug-related toxicity).
j)	Triplicate 12-lead electrocardiograms (ECGs): Three individual ECG tracings should be obtained as closely as possible in succession, but no more than 5 minutes apart. The average of the 3 readings will be used to determine ECG intervals (e.g., PR, QRS, and QT). Additional unscheduled ECG assessments should be performed in case of abnormalities and if clinical symptoms occur. Recordings should be performed prior to blood draws and prior to dosing RO7296682.
k)	Adverse Events: Prior first study drug administration only SAEs caused by a protocol-mandated intervention should be reported. After initiation of study drug all adverse events will be reported as outlined in protocol Section 8.3.1 and Section 8.3.2. Note: All AEs and laboratory safety measurements will be graded per current NCI CTCAE 5.0.
l)	For details on local laboratory assessments please refer to Appendix 4 (Clinical Laboratory Tests).
m)	Perform a serum pregnancy test for women of childbearing potential within 7 days prior to first dose. Thereafter a urine or serum pregnancy test will be performed prior to each treatment dosing with results available before dose is administered. Results must be obtained and reviewed prior to dose administration.

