4.1.5 Communication Strategy

Study Conduct: Given that this is a first-in-human trial of RO7296682, the SDEC will be utilized during the study to make recommendations regarding study conduct on the basis of trial safety data to ensure enhanced participant safety while receiving study treatment (please refer to [Appendix 1](#) for SDEC members). The SDEC will be in regular contact throughout the study by email/telephone/electronic meetings as per normal interactions during the conduct of a clinical study. When and if appropriate, the SDEC will arrange ad-hoc teleconferences or meetings to discuss the study progress with site representatives and investigators. The Sponsor (i.e., consistent of SDEC members) will be available 24 hours a day to discuss any medical or study-related issues that may arise during the conduct of the study.

In addition to the ongoing assessment of the incidence and nature of DLTs, AEs, serious adverse events, AEs of special interest (AESI), and laboratory abnormalities by the Investigators and the Medical Monitor, the SDEC will review all the cumulative data at regular intervals during the study.

The SDEC may further make recommendations regarding study conduct, including, but not limited to, the following: performing safety analyses, amending study protocol, holding participant enrollment pending further safety evaluations, enrolling additional participants at a specific dose level and schedule to obtain additional safety data, holding/discontinuing study treatment, or terminating the study.

Cohort Assignment: Upon completion of all screening evaluations and confirmation that a participant has met all eligibility criteria, investigator sites will confirm the participant's

eligibility by completing the Eligibility Screening Form. Sites will then obtain the cohort assignment from the Sponsor or from an interactive voice/web response system (IxRS) where applicable (see Section 6.3.1).

First Dose of RO7296682: After each participant receives RO7296682, the Investigator(s) must confirm to the Sponsor that the participant has been dosed and provide a brief summary of the status of the participant in terms of safety and tolerability of RO7296682. This will be communicated by email, as soon as reasonably possible and within one business day of dosing of the participant.

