Appendix 4 Clinical Laboratory Tests

The tests detailed in [Table 1](#) will be performed by the local laboratory unless otherwise specified. The results must be captured in source documentation and entered into the eCRF.

Protocol-specific requirements for inclusion or exclusion of participants are detailed in [Section 5.1](#) and [Section 5.2](#) of the protocol, respectively.

Additional tests may be performed at any time during the study as determined necessary by the Investigator or required by local regulations.

All study-required safety laboratory assessments will be performed by local laboratories, with the exception of the following:

- Analysis of IgE and tryptase samples will be performed centrally and locally.

Table 1 Protocol-Required Safety Laboratory Assessments

Laboratory Assessments	Parameters
Hematology	
 • Leucocytes, erythrocytes, hemoglobin, hematocrit, platelets, differential count (neutrophils, eosinophils, basophils, monocytes, lymphocytes, other cells).
Clinical Chemistry	
 • Sodium, potassium, chloride, bicarbonate, glucose, urea or blood urea nitrogen, creatinine, creatinine clearance (by Cockcroft-Gault formula, see Appendix 6), total protein, albumin, calcium, magnesium, phosphorous, uric acid, bilirubin, alkaline phosphatase, lactate dehydrogenase, alanine aminotransferase (ALT), aspartate aminotransferase (AST), GGT, ██████████, ferritin.
Thyroid hormones	
 • TSH, free T3 (or total T3 for sites where free T3 is not performed), free T4
Coagulation	
 • INR or PT (depending on local laboratory guidelines), activated partial thromboplastin time (aPTT); additional coagulation parameters (i.e., fibrinogen, d-dimer, anti-thrombin III [antigenic or chromogenic], fibrin degradation products) may be assessed according to clinical judgment.
Viral Serology	
 • HIV (specific tests HIV-1 antibody, HIV-1/2 antibody, HIV-2 antibody), hepatitis B surface antigen (HBsAg), total hepatitis B core antibody (HBcAb), hepatitis C virus (HCV) antibody. For participants with positive HCV antibody perform HCV RNA test.
Lipids	
 • Cholesterol, LDL cholesterol, high-density lipoprotein (HDL) cholesterol, triglycerides

Laboratory Assessments	Parameters

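### The general laboratory exception to the DLT definition has no grade cap and does not exclude liver tests, so a related asymptomatic AST, ALT or bilirubin rise, Grade 4 included, can go uncounted on the Investigator's judgement

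*Combined protocol and SAP*

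**What the plan says.** Section 4.1.3 makes any non-hematological toxicity of Grade 3 or above a DLT, apart from eight listed exceptions. Two of them can apply to liver tests:

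- **General laboratory exception.** It exempts a Grade 3 or higher "laboratory abnormality that is asymptomatic and deemed by the Investigator not to be clinically significant". It states no upper grade, no time limit and no excluded analyte.
- **Liver exception.** It exempts a transient Grade 3 rise in AST/ALT, GGT or, in participants with liver lesions, bilirubin, "that starts within 24 hours of infusion and recovers to Grade 1 or baseline within one week".

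The lead-in to the section limits DLTs to a clinically significant adverse event "or significant laboratory abnormality if all of the following events apply". The event must fall in the DLT window, be judged related by the Investigator, and not be explained by progression or another clear cause. Section 4.1.2.1 starts the window at the first administration and says it "ends 7 days after the second administration of RO7296682".

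The values themselves are kept. Table 1, footnote k, says "All AEs and laboratory safety measurements will be graded per current NCI CTCAE 5.0". Appendix 4 says "The results must be captured in source documentation and entered into the eCRF". Section 4.1.5 says "the SDEC will review all the cumulative data at regular intervals during the study".

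**The concern.** The liver exception sets objective limits on grade, onset and recovery. The laboratory exception sets none of these and turns on one judgement by the Investigator. A liver-test rise that fails the first can still be exempted by the second.

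This matters because DLT frequency is a primary endpoint (Section 3, Table 3), and DLT occurrence is the outcome that updates the mCRM-EWOC model (4.1.2.1) in a first-in-human trial. With cohorts as small as three evaluable participants, one classification can be the difference between 0/3 and 1/3 at a dose level. A wrong use of the exception can only remove DLTs from the count.

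**Working it through.** The plan gives no figure that depends on this wording, so there is nothing to reproduce. The check is a reading of the rules side by side.

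**1. The example falls inside the window.** Dosing is every 21 days, so the nominal DLT window is 21 + 7 = 28 days. Take a related, asymptomatic Grade 4 ALT rise that starts on Day 8, seven days after the first infusion. It fails the liver exception on grade and on onset, whatever its duration. It meets the laboratory exception if the Investigator judges it not clinically significant.

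**2. All cases.** For a related, asymptomatic AST or ALT rise (or bilirubin with liver lesions) judged not significant:

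| Grade | Within the onset and recovery limits | Liver exception met | Laboratory exception met | DLT as written | DLT if only the liver exception applies |
|---|---|---|---|---|---|
| 3 | Yes | Yes | Yes | No | No |
| 3 | No | No | Yes | No | Yes |
| 4 | Yes | No | Yes | No | Yes |
| 4 | No | No | Yes | No | Yes |

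For bilirubin without liver lesions the liver exception never applies. All four rows are exempt as written, and all four would be DLTs if only the liver exception applied. These rows are logical cases, not frequencies.

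**3. Does the lead-in close the gap?** No. It asks for a significant laboratory abnormality, which is the same judgement again. A change to the laboratory exception alone would leave a second route to the same result.

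**4. Does another provision require the event to be counted?**

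- The catch-all DLT in 4.1.3 depends on the Investigator's opinion, after discussion with the Sponsor.
- Section 8.3.6 and Appendix 3, Section 6, cover only an ALT or AST rise combined with raised bilirubin or jaundice. They require reporting within 24 hours, not DLT status.
- Appendix 2, Section 3.1, does not make a Grade 4 laboratory value serious by itself.
- Under Appendix 3, Section 4, a value with no symptoms, treatment change or intervention is an adverse event only if the Investigator finds it clinically significant.
- Review by the Safety and Dose Escalation Committee (4.1.5) and its power to override the model (4.2) bear on study conduct and dose choice. Neither sets a rule for classifying the event.

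**5. Effect on the step size.** With no DLT the next dose may be up to 3-fold, or 3.3-fold if rounding gives a more convenient dose. Section 4.1.2.1 then says: "After 1 DLT has been observed, a dose increment of up to 100% (i.e. up to 2-fold) is allowed". If the uncounted event would have been the first DLT, the ceiling is 3/2 = 1.5 times higher than it would otherwise be (3.3/2 = 1.65 with the rounding allowance). This changes the dose given only when the ceiling, and not EWOC or clinical judgement, sets it.

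**6. Effect on the MTD.** This cannot be computed. The visible text gives no prior, target interval or overdose limit, and no rate for such events.

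**The case against.** The best case for the plan has five parts.

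- **The exceptions are alternatives.** Meeting any one suffices. The laboratory exception covers silent, unimportant values, while the liver exception covers transient Grade 3 rises that are symptomatic or significant. This is coherent, and it answers any claim that the two contradict each other. It leaves the result in the table unchanged.
- **The specific rule should prevail over the general one.** That reading would close the gap, but it is not written down. In a multicenter trial two sites could classify the same value differently.
- **Tying DLTs to significance is deliberate**, as the lead-in shows. That is fair: this is a design choice. It remains open why objective liver limits should yield to it at Grade 4.
- **An Investigator would rarely dismiss a Grade 4 ALT.** Probably so. Laboratory data are also reviewed for each participant at the escalation teleconferences, and the next dose needs agreement between Investigators and Sponsor. These points lower the likelihood; none makes the event a DLT.
- **Parts of the protocol are blacked out**, including text in 4.1.2.1 and the adverse-event management text in 8.3.8. This stands. A reader might infer that no priority rule exists anywhere, but only the visible text can be said to lack one.

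**Conclusion.** The point holds as a statement about the visible wording of 4.1.3. A related, asymptomatic AST, ALT or bilirubin rise outside the liver limits, Grade 4 included, can be left out of the DLT count on the Investigator's significance judgement. The liver limits still decide any rise that is symptomatic or judged significant, and the value stays graded, recorded and open to committee review.

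The size cannot be given as a rate or as a shift in the MTD. Any error is toward under-counting DLTs. The higher step ceiling applies only to a first DLT and only when the ceiling binds.

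Three stronger conclusions are not supported:

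- A reader might infer that most liver-test rises would escape, because the onset limit covers only about 2 of 28 window days or because three of the four table rows change. Neither count carries a probability, and the documents say nothing about when such rises occur.
- A reader might infer that the MTD will be set too high. The dose decision also uses clinical judgement and all available data, and the selected dose also rests on tolerability and PK/PD.
- A reader might infer that GGT needs its own rule, or that treated cohorts need a special re-adjudication. Neither is needed to close this gap.

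This is a worthwhile, low-cost clarification, not a flaw that invalidates the escalation.

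**What to change.** Make two edits in 4.1.3:

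1. In the laboratory exception, add: *other than AST, ALT or bilirubin, which are governed only by the liver exception below*.
2. State that a related Grade 3 or higher AST, ALT or bilirubin rise outside the liver exception is a significant laboratory abnormality for the lead-in definition.

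Apply both prospectively. Leave values already collected to the committee's routine cumulative review.

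The cost is one clause and one sentence, plus a few more DLTs. Some will be events the Investigator regards as minor, and any related Grade 3 or higher bilirubin rise in a participant without liver lesions will count. A first DLT may lower the next-dose ceiling from 3-fold to 2-fold and slow escalation. Under 6.6 the participant stops treatment by default, with a reduced dose possible if benefiting. This could reach some participants with liver metastases, for whom 6.6 otherwise tolerates certain further rises without interruption. Relatedness remains the Investigator's call, so discretion is narrowed, not removed. If the Sponsor does intend the laboratory exception to prevail for liver tests, the protocol should say so.
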